### **8.2.5. Self-monitoring of Blood Glucose**

Participants will be strongly encouraged to perform self-monitoring of blood glucose at home in order to achieve and maintain optimum glucose control during the study. This is almost always required for participants with T1DM and is good clinical practice in participants with T2DM. It is recommended that this be done at least once weekly.

Information from blood glucose self-monitoring, in addition to that provided by values of HbA1c and fasting blood glucose, will be available to investigators for decision-making regarding adjustment of diabetic medications, diet, and exercise (or, alternatively, for decision-making regarding referral of the participant to his/her health care provider for the same purpose).

### **8.3. Adverse Events and Serious Adverse Events**

The definitions of an AE or SAE can be found in [Appendix 3](#).

AEs will be reported by the participant or noted by the investigator.

The investigator and any qualified designees are responsible for detecting, documenting, and recording events that meet the definition of an AE or SAE and remain responsible for following up AEs that are serious, considered related to the study intervention or study procedures, or that caused the participant to discontinue the study intervention (see Section 7.1).

#### **8.3.1. Time Period and Frequency for Collecting AE and SAE Information**

All AEs and SAEs will be collected from the signing of the ICF until 30 days after the final visit in the study, or early termination visit, at the timepoints specified in the SoA (Section 1.3), and as observed or reported spontaneously by study participants.

Medical occurrences that begin before the start of study intervention, but after obtaining IC will be recorded on the AE eCRF.

All SAEs will be recorded and reported to the sponsor or designee within 24 hours, as indicated in [Appendix 3](#). The investigator will submit any updated SAE data to the sponsor within 24 hours of it being available.

Investigators are not obligated to actively seek AE or SAE information after conclusion of the study participation. However, if the investigator learns of any SAEs, including a death, at any time after a participant has been discharged from the study, and he/she considers the event to be

Relamorelin

reasonably related to the study intervention or study participation, the investigator must promptly notify the sponsor.

The method of recording, evaluating, and assessing causality of AEs and SAEs and the procedures for completing and transmitting SAE reports are provided in [Appendix 3](#).

### **8.3.2. Method of Detecting AEs and SAEs**

Care will be taken not to introduce bias when detecting AEs and SAEs. Open-ended and non-leading verbal questioning of the participant is the preferred method to inquire about AE occurrences.

### **8.3.3. Follow-up of AEs and SAEs**

After the initial AE/SAE report, the investigator is required to proactively follow each participant at subsequent visits/contacts. All AEs/SAEs and non-serious AESIs as defined in [Appendix 3](#) will be followed until resolution, stabilization, the event's etiology is otherwise explained, or the participant is lost to follow-up (as defined in Section 7.3). Further information on AE/SAE follow-up procedures is given in [Appendix 3](#).

The investigator is obligated to perform or arrange for the conduct of supplemental measurements and/or evaluations as medically indicated or as requested by MSP to elucidate the nature and/or causality of the AE or SAE as fully as possible. This may include additional laboratory tests or investigations, histopathological examinations, or consultation with other health care professionals.

If a participant dies during participation in the study or during a recognized follow-up period, the investigator will provide the MSP with a copy of any postmortem findings including histopathology.

New or updated information will be recorded on the originally completed eCRF.

The investigator will submit any updated SAE data to the sponsor within 24 hours of receipt of the information.

Relamorelin

**8.3.4. Regulatory Reporting Requirements for SAEs**

- Prompt notification by the investigator to the sponsor of an SAE is essential so that legal obligations and ethical responsibilities towards the safety of participants and the safety of a study intervention under clinical investigation are met.
- The sponsor has a legal responsibility to notify both the local regulatory authority and other regulatory agencies about the safety of a study intervention under clinical investigation. The sponsor will comply with country-specific regulatory requirements relating to safety reporting to the regulatory authority, IRBs/IECs, and investigators.
- Investigator safety reports must be prepared for SUSARs according to local regulatory requirements and sponsor policy and forwarded to investigators as necessary.
- An investigator who receives an investigator safety report describing an SAE or other specific safety information (eg, summary or listing of SAE) from the sponsor will review and then file it along with the investigator's brochure and will notify the IRB/IEC, if appropriate according to local requirements.

**8.3.5. Pregnancy**

- Details of all pregnancies in female participants and female partners of male participants will be collected after the start of study intervention and until 7 days after the last dose.
- If a pregnancy is reported, the investigator must inform the sponsor within 24 hours of learning of the pregnancy and must follow the procedures outlined in [Appendix 7](#).
- Abnormal pregnancy outcomes (eg, spontaneous or elective abortion, fetal death, stillbirth, congenital anomalies, ectopic pregnancy) are considered SAEs.

**8.3.6. Medical Device Incidents (Including Malfunctions)**

Medical devices are being provided for use in this study for self-administration of study intervention. To fulfill regulatory reporting obligations worldwide, the investigator is responsible for the detection and documentation of events meeting the definitions of incident, deficiency, or malfunction that occur during the study with such devices.

The definition of a medical device incident and a device deficiency can be found in [Appendix 8](#).

Relamorelin

Incidents fulfilling the definition of an AE/SAE will also follow the processes outlined in Section 8.3.3 and Appendix 3 of the protocol.

**8.3.6.1. Time Period for Detecting Medical Device Incidents**

- Medical device incidents, deficiencies, or malfunctions of the device that result in an incident will be detected, documented, and reported during all periods of the study in which the medical device is used.
- If the investigator learns of any incident at any time after a participant has been discharged from the study, and such incident is considered reasonably related to a medical device provided for the study, the investigator will promptly notify the sponsor.

The method of documenting medical device incidents is provided in Appendix 8.

**8.3.6.2. Follow-up of Medical Device Incidents**

- All medical device incidents involving an AE/SAE will be followed and reported in the same manner as other AEs (see Section 8.3.3). This applies to all participants, including those who discontinue study intervention or the study.
- The investigator is responsible for ensuring that follow-up includes any supplemental investigations as indicated to elucidate the nature and/or causality of the incident.
- New or updated information will be recorded on the originally completed form with all changes signed and dated by the investigator.

**8.3.6.3. Prompt Reporting of Medical Device Incidents to Sponsor**

- Medical device incidents will be reported to the sponsor within 24 hours after the investigator determines that the event meets the protocol definition of a medical device incident.

**8.3.6.4. Regulatory Reporting Requirements for Medical Device Incidents and Deficiencies**

- The investigator will promptly report all incidents occurring with any medical device provided for use in the study in order for the sponsor to fulfill the legal responsibility to notify appropriate regulatory authorities and other entities about certain safety information relating to medical devices being used in clinical studies.

Relamorelin

- The investigator, or responsible person according to local requirements (eg, the head of the medical institution), will comply with the applicable local regulatory requirements relating to the reporting of incidents to the IRB/IEC.

### **8.3.7. Adverse Events of Special Interest**

#### **8.3.7.1. Potential Hy's Law**

Criteria for potential Hy's law cases are as follows:

- ALT or AST  $\geq 3 \times$  ULN) AND
- Total bilirubin  $\geq 2 \times$  ULN AND
- Alkaline phosphatase  $< 2 \times$  ULN

Study site personnel must record and report every participant who meets the criteria for potential Hy's law as SAEs (see [Appendix 9](#) for detailed description on handling potential Hy's law cases and liver toxicity). Typically, all analytes will be obtained from the same sample, but they may come from multiple samples taken within a 24-hour period. This requirement applies from the time the participant signs the ICF for the study until 30 days after the last dose of study intervention.

Additional details regarding liver safety assessments and follow-up are provided in [Appendix 9](#).

#### **8.3.7.2. Inadequate Control of Diabetes: Hyperglycemia and Hypoglycemia**

The irregular and delayed emptying of the stomach in DG has a major effect on the presentation of ingested carbohydrate to the small intestine for absorption, complicating the dosing of hypoglycemic agents (including insulin) used to manage glycemia. Participants must be closely monitored for changes to their diabetes control while in the study, and events related to hyperglycemia or hypoglycemia that are considered to be clinically significant are to be reported as AEs (Section [8.3.3](#)).

Documented episode of diabetic ketoacidosis, hyperosmolar non-ketotic diabetic syndrome, or severe hypoglycemia (defined as glucose levels  $< 3\text{mm/L}$ , or  $< 54\text{ mg/dl}$ ) that are assessed as study treatment-related will lead to permanent discontinuation of study intervention.

Relamorelin

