### 2.3. Benefit/Risk Assessment

Based on RLM information obtained to date, the benefits of study participation are expected to include accelerated GE and clinically meaningful improvement in the symptoms of DG, including nausea, abdominal pain, postprandial fullness, bloating, vomiting frequency, early satiety, and vomiting severity. A potential risk of treatment is worsening of glycemic control, including the possibility of diabetic ketoacidosis occurring. However, preventive measures are in place, including special laboratory assessments to allow early recognition by investigators and participants of a change of glycemic control. Thus, blood glucose and HbA1c assessments are included in this protocol so that action (eg, adjustment of medication and diet) may be taken, if necessary, to maintain stable glucose levels while participants are self-administering RLM. This, however, might increase the incidence of hypoglycemic reactions, especially in participants with T1DM. Participants' self-monitoring of glucose levels using glucometers is expected to alert participants and investigators to the possibility of hypoglycemic events as well. See Section 4, Study Design, for details of study procedures, dose, and study design justification.

More detailed information about the known and expected benefits and risks and reasonably expected AEs associated with RLM treatment may be found in the investigator's brochure ([Relamorelin Investigator's Brochure](#)); the Investigational Directions for Use for the pen injector, the device that will be used to administer study intervention, is also provided.

Relamorelin

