### 7.1.2. Permanent Discontinuation

Permanent discontinuation of study intervention also requires discontinuation from the study. The following criteria should be evaluated:

- Special consideration should be paid to the appearance of abnormal laboratory test results suggesting severe drug-induced liver injury (DILI). Discontinuation of study intervention for abnormal liver function should be considered by the investigator when a participant meets criteria for Hy's law (see Section 8.3.7.1 and Appendix 9) or if the investigator believes that it is in the best interest of the participant.
- Documented episode of diabetic ketoacidosis, hyperosmolar non-ketotic diabetic syndrome, or severe hypoglycemia (defined as glucose levels < 3mmol/L, or < 54 mg/dl) that are assessed as study treatment-related.
- Female participants who become pregnant during the study must be discontinued from study intervention immediately and withdrawn from the study. See Appendix 7 for further details regarding follow-up of the participant through the pregnancy.

See the SoA (Section 1.3) for data to be collected at the time of study intervention discontinuation.

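### Sections 7.1.2 and 8.3.7.2 of the protocol share one glycemic stopping trigger but word its binding force differently

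*Protocol*

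**What the plan says.** Two sections of the protocol deal with stopping treatment after a serious glycemic event.

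- **Section 7.1.2 (Permanent Discontinuation)** opens with "Permanent discontinuation of study intervention also requires discontinuation from the study" and continues with "The following criteria should be evaluated". Three bullets follow. The liver bullet says "Discontinuation of study intervention for abnormal liver function should be considered by the investigator" when Hy's law criteria are met, and it refers the reader to Section 8.3.7.1 and Appendix 9. The glycemic bullet reads "Documented episode of diabetic ketoacidosis, hyperosmolar non-ketotic diabetic syndrome, or severe hypoglycemia", limited to episodes attributed to study treatment, with severe hypoglycemia set at under 3 mmol/L or 54 mg/dl. The pregnancy bullet says affected participants "must be discontinued from study intervention immediately and withdrawn from the study".
- **Section 8.3.7.2 (Inadequate Control of Diabetes)** repeats the glycemic events and then gives the consequence: events attributed to study treatment "will lead to permanent discontinuation of study intervention".

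Section 2.3 explains why these events matter: "A potential risk of treatment is worsening of glycemic control, including the possibility of diabetic ketoacidosis occurring". Appendix 3 (10.3.1) makes inadequate control of diabetes one of two adverse events of special interest, and Section 3 gives safety as the only objective.

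**The concern.** A site that needs the stopping rules will open Section 7.1.2. There the glycemic bullet has no verb of its own, so only the lead-in governs it, and the lead-in asks for an evaluation without saying what follows. Section 8.3.7.2 is explicit that the stop is permanent. A reader of the first section alone could think the decision is open, while a reader of the second could not.

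Two things are at stake. The first is patient safety: whether a participant stays on drug after such an event could depend on the section consulted. The second is the data. Leaving treatment permanently means leaving the study, so the reading chosen decides whether the participant enters the summary of treatment-emergent events leading to discontinuation (Section 9.4.1.1). It also decides whether later laboratory values, including HbA1c (Section 9.4.1.2), are collected for that participant.

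**Working it through.** No sample size, power or event count enters this point, so the check is a comparison of the current text of the two sections.

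**Step 1. Is the trigger the same?**

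| Element | 7.1.2 | 8.3.7.2 |
|---|---|---|
| Events | Ketoacidosis, hyperosmolar syndrome, severe hypoglycemia | Same |
| Attribution | Assessed as related to study treatment | Same |
| Cut-off in mg/dl | Below 54 | Below 54 |
| Cut-off in SI units | Below 3 mmol/L | Below 3, with the unit printed as mm/L |
| Stated consequence | None in the bullet; the lead-in asks for evaluation | Permanent discontinuation |

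The first three rows match. For the fourth, I assume the usual glucose conversion of about 18 mg/dL per mmol/L, which the protocol does not give: 54 / 18 = 3.0 mmol/L. The unit in 7.1.2 therefore agrees with 54 mg/dl, and mm/L in 8.3.7.2 is a slip beside the same 54 mg/dl. It creates no second threshold. Only the last row differs.

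**Step 2. Does the 7.1.2 list settle how binding the glycemic bullet is?**

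- Liver bullet: discretionary, in its own words.
- Pregnancy bullet: mandatory, in its own words.
- Glycemic bullet: no verb, only the shared lead-in.

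Under one lead-in there is thus one item where meeting the criterion does not oblige a stop and one where it does. The list has no uniform force that the glycemic item could inherit.

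**Step 3. Does anything lead the reader from 7.1.2 to 8.3.7.2?**

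The liver bullet cross-refers to 8.3.7.1 and Appendix 9, and the pregnancy bullet to Appendix 7. The glycemic bullet has no cross-reference.

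**Step 4. Would the softer reading look workable to a site?**

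It could. Section 7.1.1 allows dosing to be interrupted for an adverse event for up to 14 days. Section 8 has immediate safety concerns discussed with the sponsor to decide whether the participant continues. A site relying on 7.1.2 alone could take either route and believe it was compliant. The explicit sentence in 8.3.7.2 closes that possibility.

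**Step 5. What follows in the data?**

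Under the opening sentence of 7.1.2, a permanent stop is also a withdrawal from the study. The same event handled under the two readings would therefore differ in discontinuation status and in length of follow-up. How many participants this could concern cannot be worked out, because the protocol gives no rate of treatment-related events of these types at the study dose.

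**The case against.** The strongest reply is that nothing conflicts. Section 7.1.2 is headed as the section on permanent discontinuation, and its lead-in can be taken to mean that sites check whether a criterion is met. Section 8.3.7.2 then supplies the consequence. Nowhere does 7.1.2 say that a participant may continue after such an event. The lead-in also cannot by itself mean optional, because it covers pregnancy too, and the liver bullet needed wording of its own to become discretionary.

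Much of this stands. A reader might infer that the protocol sets two different rules for stopping. The documents do not support that, since the trigger is identical and a site that evaluates and then stops complies with both sections. Nor does the unit slip supply a second threshold.

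The reply also has a point on size. One might try to gauge the effect from the three ketoacidosis events that Section 2.2 reports for the Phase 2b study. Those events fell one on each of three doses, whereas this study uses only 10 µg BID, and Section 2.2 does not say that any of them was judged related to treatment. The number of participating sites does not help either: it shows nothing about how consistently the text is read, and sponsor contact under Section 8 would limit divergence.

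The reply does not establish that 7.1.2 is clear on its own. Its argument that the lead-in is neutral concedes that the lead-in does not fix the consequence, and the glycemic bullet has nothing else to fix it.

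**Conclusion.** The point holds as an inconsistency in binding force. One section makes the stop automatic. The section that sites would consult for stopping rules leaves the same events under an instruction to evaluate, in a list of mixed force and with no reference to the other section. The potential consequences are uneven handling of participants after a glycemic event and discontinuation counts that depend partly on site interpretation. Their size cannot be derived from the documents.

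The conclusion assumes that some sites would use 7.1.2 without also reading 8.3.7.2. A reader might also infer that the discontinuation table is already unreliable, or that glycemic harm is the established principal hazard of the drug. Neither is supported: no count of affected participants exists, and Section 2.3 speaks only of a potential risk. Differences between investigators in judging relatedness would remain whatever the wording. The matter merits correction because it bears on safety, in a study whose only objective is safety, and because the correction is small.

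**What to change.** Reconcile Sections 7.1.2 and 8.3.7.2 so that both state the same consequence for these events in the same words. Cross-refer the glycemic bullet of 7.1.2 to 8.3.7.2, as is already done for the liver bullet. Mark in 7.1.2 which items are mandatory and which are left to investigator judgment. Correct mm/L to mmol/L in 8.3.7.2. Which consequence is clinically right is for the sponsor to decide; this review takes no position on it.

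The cost is a wording change in two sections and a communication to sites. No assessment, visit or analysis needs to change.

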### 8.3.8. Medication Errors

Medication error refers to any unintended error in the dosing and/or administration of the study intervention as per instructions in the protocol. Medication errors generally fall into 4 categories as follows:

- Wrong study drug/device
- Wrong dose (including dosing regimen, strength, form, concentration, amount)
- Wrong route of administration
- Wrong participant (ie, not administered to the intended participant)

Medication errors include occurrences of overdose and underdose of the study intervention.

Overdose: Unintentional administration of a quantity of the study intervention given per administration or per day that is above the maximum recommended dose (10 µg BID or 20 µg/day) according to the reference safety information or protocol for the study intervention or comparator as applicable. This also takes into account cumulative effects due to overdose.

Underdose: Unintentional administration of a quantity of the study intervention given per administration or per day that is under the minimum recommended dose according to the reference safety information or protocol. Since there is no clinical information on the efficacy of RLM at a dose less than 10 µg BID, a dose of 10 µg once daily will be considered an underdose.

### 8.4. Treatment of Overdose

The sponsor does not recommend specific treatment for an overdose.

In the event of an overdose, the investigator must:

1. Contact the MSP immediately.
2. Closely monitor the participant for any AE/SAE and laboratory abnormalities until study intervention can no longer be detected systemically.
3. Document the quantity of the excess dose as well as the duration of the overdose in the site's source documents for the participant.

Decisions regarding dose interruptions or modifications will be made by the investigator in consultation with the MSP based on the clinical evaluation of the participant.

Relamorelin

**8.5. Pharmacokinetics**

Pharmacokinetic parameters are not evaluated in this study.

**8.6. Pharmacodynamics**

PD parameters are not evaluated in this study.

**8.7. Genetics**

Genetics are not evaluated in this study.

**8.8. Biomarkers**

Biomarkers or other assessments are not used in the study.

**8.9. Health Economics**

Health economics outcomes will not be captured in this study.

**9. Statistical Considerations****9.1. Statistical Hypothesis**

There is no specific statistical hypothesis in this study.

**9.2. Sample Size Determination**

There were no sample size calculations performed for this study.

**9.3. Population for Analyses**

The analysis populations will consist of participants as defined in [Table 9-1](#).

